3. Abnormal ALT (≥ 5 X ULN) on day -3. (This criterion is to be assessed at study enrollment, but it will be confirmed again prior to the first dose of maraviroc)
4. Individuals who are HIV positive will not be enrolled in the study.

Treatment Plan

Dose and schedule of Maraviroc administration-

Maraviroc administration will start on day -3 and will end on day +30 after stem cell transplant, making the total number of days of drug administration 34 days. Our goal is to have steady state Maraviroc concentrations before stem cell infusion (on day 0) and continuing during the period of engraftment. The day of planned stem cell infusion will be recorded as day zero. If the stem cell infusion is given over 2 days, the first of those 2 days will be considered as day zero. Maraviroc will be administered twice daily orally or via enteral tube. Maraviroc absorption is somewhat reduced with ingestion of a high-fat meal; however, it can be given with or without food.

Dosing of Maraviroc will be based on body surface area, which will be assessed prior to starting maraviroc. This is based on the current congenital HIV trial using Maraviroc. We hypothesize that the optimal dose and exposure (as measured by the area under the concentration-time curve; AUC) for GVHD prophylaxis will likely conform to the optimal dose for the congenital HIV population (Table1). However, we recognize that stem cell transplant patients are more highly catabolic and have significantly more

concomitant medications than HIV patients, so are aware that we may find important PK differences.

BSA (m ²)	Dose of Maraviroc to be administered orally
<0.22	40 mg bid
0.2-0.43	100 mg bid
0.44-0.72	200 mg bid
0.73-1.19	300 mg bid
1.20-1.30	300 mg bid
1.31-1.73	300 mg bid
>1.73	300 mg bid

Table 1. Dosing of Maraviroc based on BSA [32].

Drug interactions with maraviroc occur with strong CYP3A4 inducers and inhibitors so these may not be used during the period of administration of maraviroc.

Enzyme Inducers	Enzyme Inhibitors
Carbamazepine	Amiodarone
Phenobarbital	Clarithromycin/Erythromycin
Phenytoin	Azoles (Keto/ Itra/ Vori/Posaconazole)
Rifampin	Verapamil
Rifabutin	Diltiazem
St. John's Wart	Grapefruit Juice
	Antiretroviral medications

Table 2. List of concomitant medications (CYP3A4 inducers and inhibitors) not allowed at enrollment or during study treatment

Adverse effects of Maraviroc

For a complete list of adverse effects, please see page 18 of protocol [23].

Study design-

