For the first part of the study, where full AUC analysis will be performed to verify the dose, we anticipate initially enrolling 12 patients to achieve 12 dose verifications. Any patients who do not achieve a complete PK data profile (i.e. due to suboptimal dose or incomplete course of study drug) will be replaced to achieve 12 dose verifications. The total number of patients will still remain 65 (Phase I and Phase II). The age of enrollment for these patients will be limited to 2-12 years old. This age restriction has been imposed because adult dosing for maraviroc in the stem cell transplant setting has already been established and it is likely that teenagers metabolize the drug similar to adults. The second part of the study, where full AUC analysis will not be conducted, will enroll the remaining patients between the ages 2-40 years.

We will enroll eligible patients and maraviroc will be administered as per study rules. Area under the concentration-time curve (AUC) determination will be performed on days 0 +/- 3 days and 10 +/- 3 days to account for weekends, national holidays or clinical deterioration not allowing for scheduled blood draws on the specified days. PK analysis will be performed after the first 3 patients. As per our study design graph, this is not an "interim" analysis, but an analysis to verify PK target attainment which then will drive either further observation or dose escalation. See Figure 1.

[figure not shown]

Figure 1. Study design

Pharmacokinetic measurement and analysis-

Blood for PK will be collected on day 0 +/- 3 days and Day 10 +/- 3 days. Complete PK profile (full AUC) will be performed on these days (see time points below). Evaluation of maraviroc trough levels will also be done routinely on all patients on study on days 0,7,14 and 21 in order to collect additional PK data, verify compliance and allow for additional dose corrections if necessary.

Target AUC/12 hours= $\geq 100\text{ng/mL}$ (based on HIV data)

PK processing will be performed at University of North Carolina's Clinical Pharmacology and Analytical Chemistry Laboratory using mass spectrometer with HPLC separation.

Plasma Maraviroc concentration data will be analyzed by compartmental and non-compartmental analysis with the help of [name], Director of Pediatric Pharmacology Research Unit (PPRU) at CCHMC, and parameter estimates generated will include clearance, half-lives, and volume of distribution along with area under the curve (AUC).

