Skin	No rash	Rash < 25% BSA	Rash 25-50% BSA	> 50% BSA or generalized erythroderma	Bullae or desquamation
GI	< 500 ml diarrhea	501-1000 ml diarrhea/day	1001-1500 ml diarrhea/day	> 1500 ml diarrhea/day	Abdominal pain and ileus
Liver	Bilirubin < 2 mg/dL	2.1-3 mg/dL	3.1-6 mg/dL	6-15 mg/dL	> 15 mg/dL

Grading		Grade 1	Grade 2	Grade 3	Grade 4
Skin		1	2	3	4
GI		0	1-2	3	4
Liver		0	1-2	3	4

Table 5. Grading and staging of GVHD.

Diagnosis of GVHD is mostly clinical and as such will be on the discretion of the treating physician. Biopsies may aid the diagnosis whenever clinically indicated but are not required in the study.

Clinical Data to be Collected and Reported:

Patients' medical information will be systematically and prospectively collected as is usual for all SCT patients. The data collected will include, but not be limited to-

1. Demographics including age, gender, weight, and height.
2. Underlying diagnosis
3. Specifics of HCT (preparative regimen, type of graft, cell dose, GVH prophylaxis, HLA type and donor relation etc.).
4. Details of engraftment (timing, failure to engraft, loss of graft)
5. Adverse effects directly related to maraviroc and transplant course
6. Onset of GVHD, grade, organ involved and treatments used by day +100
7. Whole blood donor chimerism
8. Infectious complications which include asymptomatic viremias for EBV, Adenovirus, CMV, and viral disease, bacterial and fungal infections as documented by blood cultures or bronchoalveolar lavage cultures/PCRs.
9. Overall survival at day +100
10. Incidence of relapse of primary disease by day +100

Study calendar

All testing below is part of standard evaluation for all patients undergoing allogeneic stem cell transplant and is not dependent on study enrollment, unless marked by “*”

	Enrollment	D-3	D 0 (± 3 days)	D +7 (± 2 days)	D+10 (± 3 days)	D+14 (± 3 days)	D+21 (+ 3 days)	D+30 (+ 7 days)	Monthly after day +30 until day+ 100 (± 7 days)
Informed Consent*	x								
History and physical examination	x	x	x	x	x	x	x	x	x
GVHD prophylaxis	x	x	x	x	x	x	x	x	x
CYP3A4 enzyme inducers or inhibitors *	x	x	x	x	x	x	x	x	
Acute GVHD evaluation and treatment								x	x
Full AUC analysis (dose verification part)*			X		X				
pK trough*			X	x		x	x		
pD*	X		X			X			
LFTs/CBCD/ Renal profile	x	x	x	x	x	x	x	x	x
Adverse event evaluation*		Continuous							
Compliance*		x	x	x	x	x	x	x	
Chimerism(whole blood)								x	Day + 100
Survival									Day + 100

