Study calendar for blood draws for patients undergoing formal AUC analysis-

Days	AUC	Trough drug level	Pharmacodynamic assessment
Pretransplant			x
Day 0	X (± 3 days)		X (± 3 days)
Day 7		x (± 2 days)	
Day 10	X (± 3 days)		
Day 14		x (± 3 days)	X (± 3 days)
Day 21		x (± 3 days)	

Table 6. Study calendar for blood draws for patients undergoing formal AUC analysis

For patients enrolled after maraviroc dose has been verified, the schedule for lab draws is shown on Table 7.

Days	Trough drug level	Pharmacodynamic assessment
Pretransplant		x
Day 0	x (± 3 days)	X (± 3 days)
Day 7	x (± 2 days)	
Day 14	x (± 3 days)	X (± 3 days)
Day 21	x (± 3 days)	

Table 7- Study calendar for blood draws for patients on second phase of study (after PK study complete and dose verified)

Volume of Blood Draws-

For pharmacokinetic analysis, we will need approximately 3 ml of blood, to be collected in an EDTA tube. Real time data results will be available to allow for dosing changes to

be made after the first 3 patients. For pharmacodynamics analysis, we will need 2 ml blood in a sodium heparin tube.

Discontinuation of therapy-

Since most patients experience severe toxicities while undergoing an allogeneic SCT, it will be the investigator's responsibility to determine whether certain adverse events are related to the study drug or not based on previous studies using the agent and the current labeling. Common Terminology Criteria for Adverse Events (CTCAE) version 4.0 will be used to report toxicities.

The following events will mandate stopping Maraviroc for a specific patient;

- Grade 3 liver toxicity (ALT > 5xULN or Total Bilirubin > 3xULN) regardless of cause

Maraviroc will not be restarted in these cases.

The following events will mandate holding Maraviroc therapy on a specific patient:

1. Grade 3 or higher toxicity (exclusive of liver toxicity, see section above), not attributable to underlying disease.
2. Infection, which requires treatment with a strong CYP450 inducer or inhibitor (predicted to adversely interact with Maraviroc) such as rifampin.
3. Drop in renal function to creatinine clearance <40 ml/min as measured by GFR or cystatin C.

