The drug can be restarted at the same dose after full recovery from the AEs. Maraviroc will be discontinued if the AE recurs after re-challenge. Any grade 3 liver toxicity (ALT > 5xULN or Total Bilirubin > 3xULN) regardless of cause will lead to permanent discontinuation of Maraviroc for that patient. The study will be halted for any grade 4 liver toxicity occurring within 30 days of study drug administration without clear attributable alternative cause (see stopping rules for details). Re-challenge is not permissible in the event of Grade 3 or higher liver toxicity (ALT > 5xULN or Total Bilirubin > 3xULN) regardless of cause. Any grade 1 or 2 toxicities related to study drug will not require study drug to be held.

Early termination of study drug-

Treatment will continue unless one of the following criteria applies:

1. A dose limiting toxicity (DLT) occurs. A DLT is defined as either-
 - a.) Non-engraftment by day 30, if assessed by the investigator to be related to the study drug. Engraftment is defined as the first of three consecutive measurements of ANC>500/mcL over 3 or more days.
 - b.) Grade 4 liver abnormalities, once other causes for liver toxicity have been ruled out.
 - c.) Other grade 4-5 toxicity determined by the investigator to be related with high probability to the study drug.
2. Any grade 3 or higher liver toxicity (ALT> 5xULN or Total Bilirubin > 3xULN) regardless of cause:
 - a. Any grade 3 liver toxicity (as defined above) will lead to permanent discontinuation of Maraviroc for that patient.
 - b. The study will be halted for any grade 4 liver toxicity occurring within 30 days of study drug administration without clear attributable alternative cause. (See stopping rules for specific details.)
3. Patient decides to withdraw from the study due to inability to take the drug.
4. Poor compliance to drug (missing either 6 consecutive doses (3 days) or 12 intermittent doses in the entire administration period (< 80% compliance)).

Patients removed from study for unacceptable adverse events will be followed until the adverse event resolves or stabilizes.

Toxicity Monitoring-

Maraviroc is generally well tolerated in children as noted in the phase 1 congenital HIV trial. However, a black box warning for hepatotoxicity exists. Therefore, liver function tests will be monitored on patients while on maraviroc every 48 hours until day+30 (+ 7 days).

General concomitant medication and supportive care guidelines

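### The mandatory renal hold is written as 40 ml/min with no body-size index in a trial that enrols from age 2, so read literally it can be met after a small fall in a small child

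*Combined protocol and SAP*

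**What the plan says.** The section Discontinuation of therapy gives a numbered list introduced by "The following events will mandate holding Maraviroc therapy on a specific patient". Item 3 is "Drop in renal function to creatinine clearance <40 ml/min as measured by GFR or cystatin C". The hold is therefore compulsory, and its unit is ml/min. The same section then allows resumption: "The drug can be restarted at the same dose after full recovery from the AEs". It gives no numeric renal value for restarting.

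On who is treated, Study design says of the dose-finding patients: "The age of enrollment for these patients will be limited to 2-12 years old". The second part "will enroll the remaining patients between the ages 2-40 years".

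Body size is used elsewhere. Under Treatment Plan, "Dosing of Maraviroc will be based on body surface area, which will be assessed prior to starting maraviroc", and Table 1 lists bands from below 0.22 m² to above 1.73 m². The figure 1.73 occurs only as a cut-point in the dose tables, never as an index for renal function. The eligibility criteria contain no renal criterion, and no GFR formula is given.

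The data needed for indexing are already planned: "Demographics including age, gender, weight, and height" under Clinical Data to be Collected and Reported, and "LFTs/CBCD/ Renal profile" at every visit column of the Study calendar.

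**The concern.** Clearance in ml/min rises with body size. A value of 40 ml/min is marked impairment in a person of 1.73 m², but can be normal or near-normal function in a small child. A single unindexed cut-off applied from age 2 to age 40 is therefore not one safety rule. It is tight in the smallest patients and slightly loose in those above 1.73 m².

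What is at stake is whether a mandatory instruction means the same thing for every patient. Followed to the letter, it could interrupt prophylaxis in a small child after a change in renal function that would pass unremarked in an adult. The dose-finding part enrols only the younger ages, so the question arises there first.

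**Working it through.** The 40 ml/min figure is a clinical cut-off. The document does not derive it, so there is no plan calculation to reproduce. The check is a unit conversion.

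**Inputs from the document**
- Threshold: 40 ml/min (Discontinuation of therapy, hold item 3).
- Body surface areas: 0.44, 0.72, 0.73, 1.19 and 1.73 m² are band edges in Table 1. The values 0.60 and 0.90 m² are illustrative points inside bands.

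**Input assumed**
- Indexed baseline GFR, G, in ml/min/1.73 m². The document gives none, so 90, 100, 120 and 140 are shown, with 120 as the working case.

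**Step 1: what 40 ml/min means at each size**

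Indexed equivalent = 40 × 1.73 / BSA = 69.2 / BSA.

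- 0.44 m²: 69.2 / 0.44 = 157.3
- 0.60 m²: 69.2 / 0.60 = 115.3
- 0.72 m²: 69.2 / 0.72 = 96.1
- 0.73 m²: 69.2 / 0.73 = 94.8
- 1.19 m²: 69.2 / 1.19 = 58.2
- 1.73 m²: 69.2 / 1.73 = 40.0

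The written number and an indexed 40 agree only at 1.73 m². At 2.0 m² the written rule is slightly laxer (69.2 / 2.0 = 34.6).

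**Step 2: proportional fall needed to reach 40 ml/min**

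Baseline in ml/min = G × BSA / 1.73. Fall = 1 − 40 / baseline.

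Working case, G = 120:
- 0.60 m²: baseline 120 × 0.60 / 1.73 = 41.6; fall 3.9%
- 0.72 m²: baseline 120 × 0.72 / 1.73 = 49.9; fall 19.9%
- 1.73 m²: baseline 120; fall 66.7%

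Full range:

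| BSA (m²) | G = 90 | G = 100 | G = 120 | G = 140 |
|---|---|---|---|---|
| 0.60 | starts at 31.2 | starts at 34.7 | 3.9% | 17.6% |
| 0.72 | starts at 37.5 | 3.9% | 19.9% | 31.3% |
| 0.90 | 14.6% | 23.1% | 35.9% | 45.1% |
| 1.73 | 55.6% | 60.0% | 66.7% | 71.4% |

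Cells marked with a starting value are already below 40 ml/min. The item speaks of a drop to the threshold, so these cells are ambiguous and are not counted as triggered. At 0.44 m² all four baselines fall in this group (22.9, 25.4, 30.5 and 35.6 ml/min).

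**Step 3: what an indexed threshold would mean in ml/min**

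Absolute equivalent of an indexed 40 = 40 × BSA / 1.73: 10.2 at 0.44 m², 16.6 at 0.72 m² and 40.0 at 1.73 m².

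**The case against.** The strongest reply is that the missing suffix may be shorthand. This is one children's hospital, the renal profile is part of its routine evaluation, and the item never says that the value is absolute. If the laboratory reports per 1.73 m² and clinicians read the rule that way, every difference in the working disappears. That stands as a limit on the practical effect. It does not remove the point, because the instruction is mandatory, the only unit it states is ml/min, and nothing else in the document supplies the index.

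A second reply is that the rule errs on the safe side in small children and that the drug can be resumed. That also stands, and it keeps the point minor.

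A third is that the larger falls in the table, such as 31% at 0.72 m² or 45% at 0.90 m², are real declines that may deserve a hold. Agreed. The point rests on the inconsistency across body sizes and on children who start just above 40 ml/min.

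Some stronger readings are tempting but not supported:
- **Children whose normal value is below 40 are held automatically.** The item requires a drop, so the text leaves these cases open.
- **The item fixes no unit, or accepts three methods in different units.** It names one quantity in one unit, with two ways of measuring it.
- **A renal hold turns into permanent discontinuation under the missed-dose limit in Early termination of study drug.** That limit is headed as poor compliance, and nothing says that doses withheld on instruction count towards it.
- **The written threshold is several times too high for small children.** That presumes an indexed 40 is the right paediatric value, which the document neither states nor derives.
- **Children of 0.44 m² or less will enrol because Table 1 has rows for them.** The table comes from a paediatric HIV source, and the document gives no body surface area by age.

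**Conclusion.** The point holds as a minor defect in a threshold that the trial acts on. Read as written, the renal hold represents very different losses of function by body size. At an assumed indexed baseline of 120 the triggering fall is about 4% at 0.60 m², 20% at 0.72 m² and 67% at 1.73 m². With baselines from 90 to 140 the pattern is the same, although several small-child cases become ambiguous because the starting value is already below 40 ml/min.

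The conclusion rests on two things: the assumed baselines, and a literal reading of ml/min. Without a body-size distribution in the document, no count of affected patients can be given. A reader might infer damage to the efficacy result or to safety stopping. The document does not support this: the hold enters neither the day +100 GVHD test, nor the sample-size calculation, nor any of the listed stopping rules.

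**What to change.** Restate hold item 3 as: estimated or measured GFR (including cystatin C-based) below 40 ml/min/1.73 m². The restart provision can stay as it is; no separate numeric renal restart threshold is needed.

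The cost is one line in an amendment. Weight, height and the renal profile are already collected, and body surface area is already assessed before the first dose, so no new measurement is required. If the site already works with indexed values, the change only records existing practice.

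The downside is that the hold becomes less conservative in small children than the literal text. An indexed 40 corresponds to 16.6 ml/min at 0.72 m², against the written 40 ml/min. The sponsor's clinicians should therefore confirm that an indexed 40 is the value they intend before the line is changed.

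### The poor-compliance rule equates 12 missed doses with under 80% compliance, but 12 missed of 68 planned doses is 82.4%; 14 is the first count below 80%

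*Combined protocol and SAP*

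**What the plan says.** The section Early termination of study drug lists the reasons for ending maraviroc in an individual patient. Item 4 is poor compliance, and it has two triggers. The first is "missing either 6 consecutive doses (3 days"). The second is "12 intermittent doses in the entire administration period (< 80% compliance").

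The schedule is in Treatment Plan, under the dose and schedule of maraviroc. On timing, it says "Maraviroc administration will start on day -3 and will end on day +30 after stem cell transplant". It also gives the resulting length of treatment in words: "making the total number of days of drug administration 34 days". On frequency, "Maraviroc will be administered twice daily orally or via enteral tube".

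**The concern.** The second trigger gives one threshold in two forms, a number of missed doses and a percentage. They should describe the same patients. The criterion names the whole administration period as its base, and the protocol fixes the length of that period and the dosing rate, so the percentage can be checked directly. The percentage is wrong for the count it describes.

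The criterion is operative: meeting it ends prophylaxis for that patient. The study calendar has compliance assessed at each scheduled visit from day -3 to day +30, so staff will apply the rule repeatedly. At 12 or 13 missed doses, someone following the count ends the drug, and someone following the percentage over the full course continues it. A monitor comparing case report forms with source could call either action a deviation. A report describing patients taken off drug under this item as less than 80% compliant would misdescribe those who stopped at 12 or 13.

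**Working it through.** **Inputs**

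- Administration period: day -3 to day +30 inclusive, 3 + 1 + 30 = 34 days, which matches the protocol's own total (Treatment Plan).
- Rate: two doses a day (Treatment Plan). Item 4 confirms this by equating 6 doses with 3 days.
- Threshold: 12 missed doses, labelled as below 80% (Early termination of study drug, item 4).

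**Planned doses:** 34 × 2 = 68.

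**Compliance** = (planned − missed) / planned.

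**Trying to reproduce the label.** The stated inputs do not give a figure below 80% for 12 missed doses. The table adds other denominators that might have been meant.

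| Planned doses | 12 missed | 13 missed | 14 missed | First count below 80% |
|---|---|---|---|---|
| 68 (34 full days) | 82.4% | 80.9% | 79.4% | 14 |
| 67 (one half day) | 82.1% | 80.6% | 79.1% | 14 |
| 66 (half day at each end) | 81.8% | 80.3% | 78.8% | 14 |
| 62 (day 0 to +30 only) | 80.6% | 79.0% | 77.4% | 13 |
| 60 (a 30-day course) | 80.0% | 78.3% | 76.7% | 13 |

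For 12 missed doses to be below 80%, (N − 12)/N < 0.80 must hold, so N < 60. At N = 59 compliance is 47/59 = 79.7%; at N = 60 it is exactly 80.0%, which is not below 80%. A denominator of 59 or fewer conflicts with 34 days of twice-daily dosing. The 12 may have come from a 30-day course, but that is a guess; the protocol does not say.

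**Reading 12 as more than 12** does not help: 13 missed of 68 is still 80.9%.

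**Doses due to date.** The protocol does not say whether compliance is judged on the full course or on doses due so far. If it is the latter (an assumption):

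- 12 missed is below 80% up to 59 doses due. Dose 59 is the first dose of day +26.
- 13 missed is below 80% when N < 65, that is up to 64 doses due (51/64 = 79.7%; 52/65 = 80.0%). Dose 64 is the second dose of day +28.

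On that reading the count and the label conflict only in the last few days of treatment.

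**The case against.** The strongest reply is that the count is the rule and the percentage is only a gloss. Item 4 gives two explicit counts and contains no separate instruction to stop below 80%, so a site that follows the numbers stops at 12. This largely stands, and it is the main reason the point is minor.

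It can also be said that nothing else depends on the figure. The endpoint list names feasibility but attaches no compliance cut-off to it. The Statistical analysis section decides which phase I patients enter further analysis by dose level and pharmacokinetic attainment, not by compliance. Patients in the dose-verification part are replaced for an incomplete pharmacokinetic profile, with no percentage given. This stands too.

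A third reply is that 68 need not be the denominator. A rule applied during treatment might use doses due to date, and then the label is right for most of the course. Item 4's own reference to the whole administration period points to the fixed total instead. Separately, Discontinuation of therapy requires the drug to be held for certain toxicities, interacting anti-infective treatment or reduced renal function. If held doses were removed from the denominator, a hold of 9 doses would leave 68 − 9 = 59, and 12 missed would then be below 80%. The protocol does not say that held doses are removed, and the label is still wrong for an uninterrupted course. This reply limits how far the claim that the percentage stops nobody before 14 can be taken, and it shows that the denominator needs to be written down.

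**Conclusion.** The concern holds. For the full course that the protocol defines, 12 missed doses is 82.4% compliance, 2.4 percentage points above the stated limit. Thirteen missed is 0.9 points above it, and 14 is the first count below it. The result rests on 34 days at two doses a day, both stated in the protocol, and on the full course as the base. It is unchanged with 66 or 67 doses.

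The consequence is small. The two forms of the rule disagree only for patients with 12 or 13 missed doses who have not already met the consecutive-dose trigger. If compliance is judged on doses due to date, they disagree only late in treatment. The documents do not allow an estimate of how many patients this would be. The trial's validity is not in question; this is an internal contradiction in a criterion for ending study drug, of low severity.

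**What to change.** In item 4, state that compliance is calculated on the 68 planned doses. Then take one of two routes:

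- if below 80% is the intended limit, change the count from 12 to 14 intermittent missed doses;
- if 12 is the intended limit, keep it and replace the label with about 82% (12 or more missed means 82.4% or less).

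In the same edit, say whether doses held under Discontinuation of therapy count as missed, are taken out of the denominator, or neither, because 68 alone does not settle that.

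The cost is a wording change to one criterion, with no change to the design, sample size or analysis.
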